14 STATISTICAL AND ANALYTICAL PLANS

Data analysis will be performed by the investigator.

14.1 Sample Size and Power

Planned enrollment is a minimum of 6 and a maximum of 10 subjects in this study. If a high enough proportion of subjects demonstrate a response (e.g. 5 of 6 or 6 of 8) early on in the trial, we may be able to limit the sample size, since the 95% confidence intervals would indicate a high certainty that this therapy is worth pursuing in a larger randomized controlled trial. If, however, none of the 10 subjects exhibit a response, then we can be almost certain that this particular therapy is futile, since the resulting 95% confidence interval around the response rate would range from 0% to 31%.

14.2 Statistical Analyses

Data will be summarized descriptively for each subject. No formal comparative statistical analyses are planned

14.3.1 Background Characteristics

14.3.1.1 Subject Disposition

The number of subjects in each disposition category (e.g., enrolled; prematurely discontinued from the study; and completed the study) will be summarized.

14.3.1.2 Demographics and Baseline Characteristics

The following demographic and baseline characteristics will be captured (as appropriate): *CFTR* genotype, sex, race, age, weight, height, BMI, spirometry, SGRQ, CFQ-R, QOL-B, and sputum culture results.

14.3.1.3 Prior and Concomitant Medications

Medications taken during the collection period specified in Section 11 will be summarized by preferred term using the World Health Organization Drug Dictionary (WHO-DD) for the Safety Set as frequency tables in 2 parts:

- Prior medication: medication that started before the first dose of inhaled nitric oxide regardless of when dosing of the medication ended.
- Concomitant medication: medication received at or after the first dose of inhaled nitric oxide, medication that was received before initial dosing of and continued after initial dosing, or medication with missing stop date.

Medications that started before the first dose of inhaled nitric oxide and continued after the first dose of inhaled nitric oxide will be summarized separately as prior medications and concomitant medications, respectively. Medications with a missing start date will be considered to have a start date before the first dose of inhaled nitric oxide.

14.3.2 Efficacy Analysis

For the primary analysis, the proportion of subjects with culture conversion (negative) will be recorded. For the secondary analysis the change (absolute change) in semi-quantitative cultures from baseline will be calculated as post-baseline value – baseline value. Exploratory analysis will be the change in time-to-detection as reported in the broth culture system.

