MEDICAL UNIVERSITY OF SOUTH CAROLINA

Study Protocol

**A Proof of Concept Study of Inhaled Nitric Oxide for Adults
with Pulmonary Non-Tuberculous Mycobacterial Infection**

IND Number: 140649

Date and Version of Protocol: October 01, 2019

(Version 3.0)

NCT #: 03748992

IRB approved on 18SEP2018

Title	A Proof of Concept Study of Inhaled Gaseous Nitric Oxide (gNO) for Adults with Pulmonary Non-Tuberculous Mycobacterial (NTM) Infection
Clinical Phase	Phase 2
Objective	To evaluate the efficacy and safety of open-label exposure of gNO in patients with NTM lung disease
Endpoints	
Primary
 
 • Culture growth (positive or negative) at end of treatment (EOT) compared to baseline 
Secondary
 
 • Safety and tolerability assessments based on adverse events (AEs), clinical values (i.e., methemoglobin levels) • Semiquantitative mycobacterial culture results comparing EOT to baseline 
Exploratory
 
 • Time to positive mycobacterial cultures comparing EOT to baseline • Measures of systemic inflammation comparing EOT to baseline • Absolute change in quality of life scores from baseline to EOT
Study Population	Adult subjects with NTM lung disease and persistently positive mycobacterial sputum cultures
Number of Subjects	10
Number of sites	2
Study Duration	Subjects will be treated for 3 weeks (5 days per week) and followed monthly for 3 months
Study Design	This 2 study is designed to evaluate the efficacy and safety of open-label gNO treatment in subjects with NTM lung disease and persistently positive sputum cultures growing NTM. This is a proof-of-concept study in which all subjects will be treated with gNO (i.e. no control) to see if there can be a microbiological effect by conversion to negative sputum cultures and how long that effect can be sustained following treatment. In addition, this study will assess the feasibility of such a treatment course in this patient population and measure relevant clinical outcomes (e.g. cough, quality of life). Subjects will provide sputum for culture at baseline, weekly during treatment, and monthly for 3 months following treatment to assess if there is persistence of infection in cultures. Safety measures will include monitoring of arterial oxygen saturation and methemoglobin levels. All serious and non-serious adverse events will be collected

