Assessments	
 • Feasibility: ability to recruit subjects, ability to complete the planned treatment, and assessment of their experience and willingness to undergo this therapy • Efficacy: sputum cultures (mycobacteria), symptom scores (cough, quality of life) • Safety: AEs, clinical monitoring assessments (pulse oximetry), vital signs, and physical examinations
Statistical Analyses	Data will be summarized descriptively for each subject. The overall response rates (culture conversion short and long term) will be calculated after each patient has completed the trial, and exact binomial confidence intervals will be constructed.

SCHEDULE OF ASSESSMENTS

Table 3-1: Schedule of Assessments

Visit	Screening	Treatment Period									Follow up Period		
		A1	A2-4	A5	B1	B2-4	B5	C1	C1-4	C5	F1	F2	F3
Day	-28-14	1	2-4	5	8	9-11	12	15	16-18	19	W7	W11	W15
Informed consent	x												
Medical history	x												
Demographics ^a	x												
Physical examination	x	x			x			x			x	x	x
Height and weight	x				x			x			x	x	x
Vital signs	x	x	x	x	x	x	x	x	x	x	x	x	x
Symptom score ^b	x			x			x			x	x	x	x
Safety labs ^c	x									x			
CRP	x									x			
Spirometry ^d	x	x ^d			x ^d			x ^d					
Sputum cultures ^e	x			x			x			x	x	x	x
Echocardiogram	x												
Pulse oximetry	x	x	x	x	x	x	x	x	x	x	x	x	x
MetHb measurement	x	x	x	x	x	x	x	x	x	x			
gNO dosing		x	x	x	x	x	x	x	x	x			
Adverse events		x	x	x	x	x	x	x	x	x	x	x	x
Concomitant medications	x	x	x	x	x	x	x	x	x	x	x	x	x

^a Demographics include sex, race, and age. Baseline characteristics include diagnosis, and if CF include *CFTR* genotype

^b Symptom scores will include cough score (Leicester), quality of life (SGRQ, CFQ-R, QOL-B), as appropriate for the underlying diagnosis (i.e. CF subjects will complete the CFQ-R and SGRQ; other subjects will complete the QOL-B and SGRQ)

^c Safety labs include comprehensive metabolic panel (to include creatinine, AST, ALP, ALT and chemistry), complete blood cell count with differential, GGT, PT/INR, 6-GPD level, and urine pregnancy test (if applicable)

^d Spirometry will be performed pre and post first treatment of the day

^e Sputum will be tested for bacteria and mycobacteria (including AFB smear and culture). Susceptibility testing will not be performed

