In sum, there is sufficient preclinical evidence of antimicrobial effect of gNO on NTM. There are compelling reasons to use a gas for treatment as it may get to areas of the lung that will not be reached by antibiotics by either the systemic or inhalation route. Even in poorly ventilated lung units, a 50 minute exposure should be sufficient time for NO to achieve therapeutic levels. There are also sufficient safety data that the proposed exposure should be well tolerated. It is premature to predict how this therapy will be best used, but multiple options could be conceived such as eradication of first infection (especially for Mabs), improving outcomes when used in conjunction with standard antibacterial regimens, shorter durations of treatment regimens, among others. This study proposes to demonstrate that there can, indeed, be a killing effect of NTM as well as assess for how quickly it may return in sputum cultures as these will be key factors in designing subsequent treatment trials.

7 **STUDY OBJECTIVE**

The short term goal of this proposal is a proof-of-concept study in which we will expose patients with NTM lung disease and who have persistently positive sputum cultures to test the feasibility of this therapy in this population as well as the safety and efficacy of the therapy.

8 **STUDY ENDPOINTS**

- The primary measure of efficacy will be sputum culture for mycobacteria converted to negative at completion of treatment.
- Secondary measures of efficacy will include assessment of feasibility of this treatment (i.e. recruitment, completion, and satisfaction), sputum culture results for mycobacteria at 3 months following completion of treatment, and safety and tolerability assessments based on adverse events (AEs) and point of care testing for arterial oxygen saturation and methemoglobin levels.

9 **STUDY DESIGN**

9.1 **Overview of Study Design**

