This open-label treatment of NTM lung disease is a proof-of-concept study to assess the efficacy of gNO in reducing the burden of NTM in patients known to have persistently positive sputum cultures. The patients will have documented NTM lung disease and meet inclusion criteria of persistently positive sputum cultures even if on antimicrobial therapy. The study is designed to evaluate the feasibility, efficacy and safety of open-label gNO in this population. Feasibility will be assessed by ease of recruitment and completion of the study, as well as a survey of the subjects' experience with the treatment and their willingness to use this as a therapy. Efficacy will be assessed by the results of sputum cultures for mycobacteria, looking at the short term effect (i.e. conversion to negative while on treatment) as well as the long-term effect (i.e. looking at the duration of culture conversion after treatment). Subjects will undergo sputum cultures at baseline and weekly during treatment, and monthly for 3 months following completion of therapy. Additional measures will include symptom scores of cough and quality of life. Safety will be assessed by monitoring of SaO₂ and metHb levels while on treatment. All serious and non-serious adverse events will be collected.

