9.2 Rationale for Study Design

This is a proof-of-concept study based upon *in vitro* exposure of NTM to gNO. The primary efficacy measure (conversion to negative mycobacterial cultures) are expected to change in the short term (i.e. during the 3 week treatment period), but assessment after completion of treatment is important to determine if there is a return to culture positivity in the immediate term post-treatment. The overall culture response rate and the time to recurrence (if it recurs) will be important data to determine if this therapy has clinical potential for this patient population and the resulting data will be helpful for estimating the effect size to be used in designing a future randomized controlled trial

The other key measures include reduction in the mycobacterial density (in the event that cultures do not convert to negative, this will provide information about some treatment effect), efficacy based on symptoms, safety, and the feasibility of conducting a larger trial or whether this therapeutic regimen would have viability.

As this is a proof-of-concept study, there is no value to a blinded aspect for the study.

NO-NTM

Treatment will be open-label and clinical outcomes will be assessed by the individuals.

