10 SELECTION OF STUDY POPULATION

10.1 Inclusion Criteria

Patients with NTM lung disease who persistently demonstrate infection with positive sputum cultures will be eligible for the study. This will include patients with and without CF as this is typical of the NTM population and this therapy should be non-discriminatory. Inclusion criteria are as follows:

- Subjects are ≥ 18 years of age and able to provide informed consent.
- Subjects have NTM lung disease as defined by each of the following:
 - Sputum cultures positive for NTM (MAC or *M. abscessus*)
 - Radiologic studies that demonstrate features consistent with disease such as nodular bronchiectasis and/or cavities
 - Symptoms consistent with disease including respiratory (e.g. cough, sputum production, hemoptysis, chest pain) and constitutional (e.g. fevers, night sweats, fatigue, myalgias, arthralgias, weight loss)
- Subjects are able to produce sputum for culture (either spontaneous or induced).
- Subjects have a history of persistently positive sputum cultures for NTM defined as
 - ≥ 2 positive cultures over the preceding 6 months AND
 - Has not met the definition for culture clearance in the last 6 months (three negatives in a row)
- Clinically stable with no significant changes in health status within 14 days prior to Screening or Day 1
- Subjects are willing and able to perform requirements of the study.

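### Section 14.1 draws firm go and futility conclusions from a single-culture, uncontrolled response rate without stating any background rate of negative cultures

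*Combined protocol and SAP*

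**What the plan says.** **Endpoint.** Section 8 states: "The primary measure of efficacy will be sputum culture for mycobacteria converted to negative at completion of treatment". Table 3-1 and Section 12.4.1 schedule one sputum collection at end of treatment (EOT), on Day 19. Section 14.3.2 then reads: "For the primary analysis, the proportion of subjects with culture conversion (negative) will be recorded". It names no denominator. The Synopsis adds exact binomial intervals and says "The overall response rates (culture conversion short and long term) will be calculated after each patient has completed the trial".

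**Comparator.** The Synopsis says "all subjects will be treated with gNO (i.e. no control", and Section 14.2 plans no formal comparison. Section 14 gives no rate of negative cultures expected without gNO.

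**Entry.** Section 10.1 asks for at least two "positive cultures over the preceding 6 months AND" the condition "Has not met the definition for culture clearance in the last 6 months (three negatives in a row". The eligibility appendix under Section 10.1 lists six admissible patterns with four negatives in months 6 to 1, each with a further positive at month 0. Section 10.2 allows an anti-NTM regimen that has been stable for six months. Section 10.1 does not explicitly require the Screening culture to be positive.

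**Reading of the result.** Section 14.1 says that 5 of 6 or 6 of 8 responders (given as examples) might allow a smaller sample, because the 95% interval would make it highly certain that a larger randomised trial is justified. It treats none of 10 as all but establishing futility and cites an interval of 0% to 31%. Section 9.2 adds that "the resulting data will be helpful for estimating the effect size to be used in designing a future randomized controlled trial".

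**The concern.** A subject with intermittently positive cultures can give a negative sample on Day 19 without any effect of gNO. Such a sample counts as a response. Whether 5/6 or 6/8 is persuasive therefore depends on how often a single culture would be negative anyway, and Section 14.1 attaches its certainty without that number. The raw proportion also overstates the gNO effect if it is carried into the next trial's sample size.

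Because neither a positive Screening culture nor a denominator is stated, a subject negative at both Screening and Day 19 could be counted as converted.

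The futility sentence has a separate weakness: it claims more than an interval reaching 31% can carry.

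**Working it through.** **Inputs.** The examples 5/6, 6/8 and 0/10 and the interval 0–31% are from Section 14.1. The exact binomial method is from the Synopsis. The entry rule is from Section 10.1 and its appendix. The probability q that a single culture is negative without gNO is *not in the documents*. It is assumed over a range, with cultures independent and q the same for all subjects.

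**1. The plan's own figure.** The upper exact limit for 0/10 is 1 − 0.025^(1/10) = 30.8%, which rounds to the stated 31%. The figure is correct.

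**2. Lower limits for the go examples.** The exact lower limit is the p that solves P(X ≥ x | n, p) = 0.025.
- 5/6: 35.9% (upper limit 99.6%)
- 6/8: 34.9% (upper limit 96.8%)

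Both exclude a background of one third (33.3%). Neither excludes one half.

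**3. Chance that an inert drug meets the examples.** With X₆ negatives among the first six subjects, meeting 5/6 or, failing that, 6/8 has probability P(X₆ ≥ 5) + P(X₆ = 4) × q².
- q = 1/3: 13/729 + (60/729)(1/9) = 1.78% + 0.91% = 2.7%
- q = 1/2: 7/64 + (15/64)(1/4) = 10.94% + 5.86% = 16.8%

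**4. Inflation of the effect.** If gNO truly clears 20% of subjects and the rest are negative with probability q, the expected observed rate is 0.2 + 0.8q.

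| Assumed q | ≥5/6 | ≥6/8 | 5/6, or failing that 6/8 | True 20% appears as |
|---|---|---|---|---|
| 10% | 0.01% | <0.01% | 0.01% | 28% |
| 1/6 | 0.07% | 0.04% | 0.09% | 33% |
| 1/3 | 1.8% | 2.0% | 2.7% | 47% |
| 1/2 | 10.9% | 14.5% | 16.8% | 60% |

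**5. What the entry rule does to q.** Of the 64 possible patterns of six monthly cultures, 44 have at least two positives and no run of three negatives: 6, 16, 15, 6 and 1 patterns with 2, 3, 4, 5 and 6 positives. The six two-positive patterns are those marked eligible in the appendix. A subject with negative probability q passes with probability Σ Nₖ(1 − q)ᵏq⁶⁻ᵏ, where Nₖ is the number of eligible patterns with k positives.
- q = 1/3: 648/729 = 89%
- q = 2/3: 297/729 = 41%

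The rule admits intermittent negativity but removes many subjects in whom it is frequent.

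**6. The futility statement.** A true EOT-negative rate of 10% gives 0/10 with probability 0.9¹⁰ = 34.9%. A true rate of 20% gives it with probability 0.8¹⁰ = 10.7%.

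**The case against.** The strongest defence is that this is an openly uncontrolled, descriptive proof of concept. Section 14.1 offers its figures as examples, and the step it recommends is a randomised trial, which would supply the missing control. The Synopsis compares EOT with baseline and Section 8 speaks of conversion, so a positive baseline is implied. Weekly and follow-up cultures, semiquantitative change and time to detection will show intermittent patterns. The 0–31% interval stands in the same sentence as the futility statement.

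Much of this stands. No control arm is needed, and if q is one third or less an inert drug rarely meets the examples. But the supporting measures change neither the primary proportion nor the certainty that Section 14.1 attaches to it. The inflation in step 4 is present even at q = 10%. An implied baseline requirement is not a stated denominator.

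Three stronger readings are tempting, and the documents do not support them.

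- **Background negativity is two thirds.** At q = 2/3 an inert drug would meet the examples in 49.7% of trials. But four negatives in six is the limit for one subject, and four in seven once the month-0 positive is counted. It is not an expected average, and step 5 shows the rule working against it.
- **Pre-study cultures could supply the benchmark.** They were selected to contain positives. With two samples both must be positive, so the negative share is zero whatever q is. With six samples and q = 1/2 its expected value is 40.9%. The share runs below q.
- **The appendix's three-consecutive-negatives definition should govern.** It is written for eligibility, and the EOT meaning in Section 8 is clear. Section 9.1 describes "looking at the short term effect (i.e. conversion to negative while on treatment) as well as the long-term effect" without setting a conversion rule for the latter. A rule fixed on Weeks 7, 11 and 15 would miss a qualifying run on Day 19, Week 7 and Week 11.

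**Conclusion.** The point holds as an error of interpretation in Section 14.1 and an unstated denominator in Section 14.3.2. It is not a fault in the choice of an uncontrolled design. Results of 5/6 or 6/8 support going on only if background negativity is below about 35%, and the protocol gives no basis for that figure. The risk of a false go reading is small at q = 1/3 and material only at about one half or more. The overstatement of the effect size does not depend on a high q. The 0/10 interval is right, but near-certainty of futility does not follow from it.

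The probabilities rest on independent cultures and a common q. Where q lies in this population cannot be settled from the documents.

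**What to change.** (a) **Section 14.1.** State that 5/6 or 6/8 supports pursuing gNO only if background negativity is below about 35%. Show the inert-drug probabilities over a stated range of assumed q. Replace the futility statement with: 0/10 excludes response rates above 31%.

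(b) **Sections 8 and 14.3.2.** Label the primary outcome *culture-negative at EOT (single culture)*. Compute it in subjects with a positive Screening culture, applied at analysis and not as a new entry rule, and give the all-treated count beside it. Add that the raw proportion is not itself the gNO effect size for a later trial. The denominator rule stops a subject negative at both time points from counting as converted. It does not remove the inflation in step 4.

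The cost is wording only: no new samples, and no change to enrolment or to the EOT question. The downside is a less favourable reading of a good result and a possibly smaller denominator.

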14.3.3 Safety Analysis

All safety data will be presented in individual subject data listings.

14.3.3.1 Adverse Events

All adverse events with start date on or after enrollment date through the last study visit will be summarized. Adverse events are defined in Section 15.1.1. Adverse event summary tables will include the following:

- all adverse events;
- related (identified as related to inhaled nitric oxide by the investigator) adverse events;
- adverse events leading to treatment discontinuation;
- serious adverse events (SAEs); and
- adverse events by relationship.

Summaries will be presented by MedDRA system organ class and preferred term using frequency counts and percentages. A subject with multiple occurrences of the same adverse event or a continuing adverse event will be counted only once, by relationship.

14.4 Interim Analyses

No interim analyses will be performed but safety will be monitored throughout.

15 PROCEDURAL, ETHICAL, REGULATORY, AND

ADMINISTRATIVE CONSIDERATIONS

15.1 Adverse Event and Serious Adverse Event Documentation and Reporting

15.1.1 Definition of an Adverse Event

For this study, an adverse event is defined as any untoward medical occurrence in a subject during the study, including any newly-occurring event or previous condition that has increased in severity or frequency after the informed consent form is signed.

A subset of adverse events may meet serious criteria. The definition of an SAE and reporting procedures for SAEs are detailed in Section 15.1.2. The definitions below apply to both adverse events and SAEs.

Planned hospital admissions or surgical procedures for an illness or disease that existed before the subject was enrolled in the study are not to be considered adverse events unless the condition deteriorated in an unanticipated manner during the study (e.g., surgery was performed earlier than planned).

15.1.2 Definition of a Serious Adverse Event

An SAE is any adverse event that meets any of the following criteria:

- Fatal (death, regardless of cause, that occurs during participation in the study, or occurs after participation in the study and is suspected of being possibly related to inhaled nitric oxide).
- Life-threatening, such that the subject was at immediate risk of death from the reaction as it occurred.
- Inpatient hospitalization or prolongation of hospitalization, with the exception of planned or elective hospitalization.
- Persistent or significant disability/incapacity (disability is defined as a substantial disruption of a person's ability to conduct normal life functions).
- Congenital anomaly or birth defect.
- Important medical event that, based upon appropriate medical judgment, may jeopardize the subject or may require medical or surgical intervention to prevent 1 of the outcomes listed above (e.g., an allergic bronchospasm requiring intensive treatment in an emergency room or at home).

